# Study Protocol

## Study Aims

The goal of this study is to design, implement, and test the impact of a quality improvement (QI) intervention that uses an EHR CDS tool among physicians newly ordering an antipsychotic medication for adults with ADRD to increase guideline-concordant prescribing. The study team hypothesizes that the intervention will reduce participating clinicians' pill days per patient prescribed.

## Study Design and Setting

This study design is a pragmatic parallel arm randomized-controlled trial. The study team will randomize eligible physicians at UCLA Health, a large academic health system in Los Angeles, California, to be either exposed to the EHR CDS tool (intervention) or not (control) in a 1:1 allocation ratio over a 12-month period when they initiate a prescription for a new antipsychotic medication during a visit with a patient with ADRD.

## Ethical Considerations

The Institutional Review Board (IRB) of the University of California, Los Angeles (UCLA) approved this protocol on 01/27/2020 (IRB#19-002122). The IRB and National Institute on Aging (NIA) Data Safety Monitoring Board (DSMB) approved a waiver of informed consent because this trial is a part of ongoing quality and patient safety improvement efforts. In addition, the Principal Investigator will notify all of the study participants that this project is an NIH-funded clinical trial and provide them with the trial registration link after the study has been completed. This study has been registered in ClinicalTrials.gov, with trial registration identifier: NCT04851691.

The study data containing patient health information will be safeguarded with firewalls and encryption following UCLA IRB guidelines, as well as a unique study ID created to protect the identities of patients. If successful, UCLA plans to adopt full integration of the EHR CDS tool for all eligible clinicians.

## Methods

### Inclusion Criteria

Eligible physicians for the EHR CDS tool intervention include physicians who provide ambulatory care in the UCLA health system and have generated a new antipsychotic prescription (e.g., Quetiapine, Olanzapine, Risperidone, Aripiprazole, Haloperidol, Clozapine) for eligible patients (described below) in the UCLA health system at least once between 1/1/2019-4/30/2021 (n = 149). Based on current prescribing patterns at UCLA, we estimate that the vast majority of physicians in the study (>75%) will only see this EHR CDS tool 1–2 times over a year, suggesting little impact on clinical workflow and lessening opportunities for contamination. Eligible physicians will be enrolled in the study during their first encounter with one of the patients during which a new antipsychotic medication order is initiated.

Inclusion criteria for patients will include: 1) having an assigned primary care physician (PCP) and/or assignment to an Accountable Care Organization (ACO) at UCLA Health, and 2) being part of the health system's EHR-based dementia registry. The health system's dementia registry uses a select group of ICD-10 codes included in the patient's problem list to identify patients with ADRD, without age restrictions (Table 1). This ICD-based approach was implemented by the health system as an update to a previously published approach. To measure the specificity of this method for correctly classifying patients as having ADRD, physicians on the study team (board-certified geriatrician, palliative care specialist, and

primary care general internist) conducted an implicit review (e.g., expert clinician diagnostic judgment) on a random sample of 30 registry patients; 29 out of 30 (97%) had ADRD.

*Table 1: Dementia international classification of diseases 9th and 10th revision (ICD-9 and ICD-10) codes.*

	ICD-9 codes	ICD-10 codes
At least one code from a problem list	42, 46.11, 46.19, 46.79, 49.9, 94.9, 199.1, 277.39, 290, 290.1, 290.11, 290.12, 290.13, 290.2, 290.21, 290.3, 290.4, 290.41, 290.42, 290.43, 290.8, 290.9, 291.2, 292.82, 293, 294.1, 294.11, 294.2, 294.21, 294.8, 294.9, 296.9, 297.9, 298.9, 305.9, 310.2, 311, 319, 323.9, 330.1, 330.8, 331, 331.1, 331.11, 331.19, 331.4, 331.5, 331.6, 331.82, 331.83, 331.9, 332, 332.1, 333, 333.4, 340, 345.9, 348.1, 349.9, 369.9, 437, 440.9, 459.9, 781, 781.3, 784.3, 797, 907, 999.9, E980.5, V17.2, V40.31	A52.17, A81.00, A81.01, A81.9, A86, B20, C80.1, E75.6, E85.4, F01, F01.5, F01.50, F01.51, F02.80, F02.81, F03, F03.9, F03.90, F03.91, F05, F06.8, F07.81, F10.27, F10.97, F13.27, F13.97, F18.17, F18.97, F19.17, F19.97, F22, F32.9, F39, F84.2, G10, G20, G21.8, G23.1, G30, G30.0, G30.1, G30.8, G30.9, G31.01, G31.09, G31.83, G31.84, G31.85, G31.9, G35, G40.909, G91.2, G91.9, G93.1, G98.8, H54.7, I67.2, I67.3, I67.850, I68.0, I70.90, I80.0002, R25.2, R27.0, R41.0, R41.81, R47.01, S06.9X9S, T80.89XA, Z91.83

Consistent with prior research, patients will be excluded from eligibility if they have diagnosis codes for schizophrenic disorders, delusion disorders, bipolar disorders, or other non-organic psychoses on their problem list (Table 2). Patients with Parkinson's disease on their problem list will also be excluded because quetiapine is clinically indicated to decrease hallucinations induced by dopaminergic medications in patients with Parkinson's disease. Additionally, because the target for this intervention will be new prescriptions, if patients have been prescribed antipsychotics in the prior 12 months, they will not be eligible. Eligible encounters will include ambulatory office visits and scheduled telephone and video telehealth visits. Emergency department visits, observational stays, and inpatient hospitalizations will not be eligible for the CDS to fire.

*Table 2: ICD-9 and ICD-10 codes for exclusion criteria reflecting severe mental illness.*

Diagnosis Code Type	Diagnosis Code
ICD-9-CM	295
ICD-9-CM	295.1
ICD-9-CM	295.2
ICD-9-CM	295.3
ICD-9-CM	295.4
ICD-9-CM	295.5
ICD-9-CM	295.6
ICD-9-CM	295.7
ICD-9-CM	295.8
ICD-9-CM	295.9

ICD-9-CM	296
ICD-9-CM	296.1
ICD-9-CM	296.4
ICD-9-CM	296.5
ICD-9-CM	296.6
ICD-9-CM	296.7
ICD-9-CM	296.8
ICD-9-CM	297.1
ICD-9-CM	297.2
ICD-9-CM	297.3
ICD-9-CM	297.8
ICD-9-CM	298.3
ICD-9-CM	298.4
ICD-10-CM	F31.9
ICD-10-CM	F22
ICD-10-CM	F24
ICD-10-CM	F23
ICD-10-CM	F52.8
ICD-10-CM	F31.89
ICD-10-CM	F34.0
ICD-10-CM	F09
ICD-10-CM	F06.1
ICD-10-CM	F31.70
ICD-10-CM	F43.0
ICD-10-CM	G30.9
ICD-10-CM	F02.80

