### [Primary Outcome](#)

The primary outcome will be the cumulative total of new antipsychotic prescription days supplied by clinicians per eligible patient in the 12 months after the intervention rollout date compared to the prior 12-months, in the intervention versus control groups regardless of the number of visits the provider receives.

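### The ICD-10 half of Table 2 does not match the exclusion text: it omits codes for schizophrenia and most bipolar disorder, and it lists two dementia codes that Table 1 uses for registry entry

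*Combined protocol and SAP*

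**What the plan says.** Under Inclusion Criteria, the protocol says "patients will be excluded from eligibility if they have diagnosis codes for schizophrenic disorders, delusion disorders, bipolar disorders, or other non-organic psychoses" and points to Table 2, whose title is "ICD-9 and ICD-10 codes for exclusion criteria reflecting severe mental illness". The table gives bare codes without labels, first ICD-9 and then ICD-10.

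Entry to the trial runs through the dementia registry, which "uses a select group of ICD-10 codes included in the patient's problem list". Table 1 lists the qualifying codes in both an ICD-9 and an ICD-10 column.

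Two further exclusions stand in the same paragraph and do not cite Table 2. One is "Patients with Parkinson's disease on their problem list will also be excluded". The other is "if patients have been prescribed antipsychotics in the prior 12 months, they will not be eligible".

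The primary outcome is the "cumulative total of new antipsychotic prescription days supplied by clinicians per eligible patient". The eligibility definition therefore determines which prescriptions are counted.

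**The concern.** The text names four diagnosis groups to exclude. The first, schizophrenic disorders, is covered in ICD-9 and has no ICD-10 code at all. Bipolar disorder has three ICD-10 codes. A registry patient whose schizophrenia is recorded only under F20.x would pass the printed screen, although the text says this patient is out.

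The last two rows of the table create the opposite problem. G30.9 and F02.80 are not severe mental illness codes under the table's own title, and Table 1 uses both to admit patients. Applied as printed, they would remove people the trial is meant to reach.

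Eligible patients determine which physicians are on the randomization list (n = 149), the prescription counts that form the strata, when the alert fires, and which pill-days are counted. A wrong list would carry into all four.

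**Working it through.** No sample size, power or alpha figure bears on this point. The check sets the text beside the tables.

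**Step 1: Table 2 against the text.** The table prints no labels, so the assignment of codes to groups below uses the ordinary meaning of the ICD codes.

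| Group named in the text | ICD-9 codes printed | ICD-10 codes printed | ICD-10 codes absent |
|---|---|---|---|
| Schizophrenic disorders | 295, 295.1 to 295.9 (10) | none (0) | F20.x, F25.x |
| Bipolar disorders | 296, 296.1, 296.4 to 296.8 (7) | F31.9, F31.89, F31.70 (3) | F30.x, all other F31.x |
| Delusion disorders and other non-organic psychoses | 297.1, 297.2, 297.3, 297.8, 298.3, 298.4 (6) | F22, F23, F24 (3) | F28, F29 |
| Other rows | none (0) | F34.0, F09, F06.1, F43.0, F52.8, G30.9, F02.80 (7) | |

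Totals: ICD-9, 10 + 7 + 6 = 23 codes. ICD-10, 0 + 3 + 3 + 7 = 13 codes.

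**Step 2: Table 2 against Table 1.** Matching the 13 ICD-10 exclusion codes exactly against the 70 ICD-10 entry codes in Table 1 gives three codes in both: F22, G30.9 and F02.80.
- F22 is a delusional disorder code. Its presence in Table 2 agrees with the text, so a patient who enters the registry on F22 is then excluded. This is workable once precedence is stated.
- G30.9 and F02.80 are dementia codes. Their presence in Table 2 agrees with nothing in the text.

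**Step 3: two patients under a literal reading.**
- Patient A is in the registry on F01.50, has F20.9 on the problem list, no listed ICD-9 code, and no antipsychotic in the past year. The text excludes this patient; Table 2 does not.
- Patient B is in the registry on G30.9 and has no psychiatric diagnosis. The text includes this patient; Table 2 excludes them.

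**Step 4: what the documents allow on size.** They give no count of registry patients with any of these codes. The figure downstream of eligibility is the physician count: 149 × 0.65 = 96.85, against the stated analytic sample of 96 (48 per arm). The arithmetic is sound, but 149 was obtained by applying an eligibility definition, so it may change if the list changes. The documents do not show by how much.

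**The case against.** **The printed table may not be the working list.** No section says that the alert was built from Table 2 as printed. The two dementia rows suggest, as an inference, that the table is not a clean copy of what was used. The table also breaks across a page within its ICD-10 half, so a row lost in the PDF reading cannot be fully ruled out, although the run looks continuous. This stands, and it makes the consequence conditional. It does not remove the point, because the plan gives no other list.

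**The 12-month rule already removes most such patients.** This largely stands for the missing codes. Anyone with schizophrenia or bipolar disorder who had an antipsychotic in the past year is out whatever the code, which leaves those untreated for a year and then newly started. It does nothing for patients wrongly removed through G30.9 or F02.80.

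**The registry was validated.** Chart review confirmed dementia in 29 of 30 sampled registry patients. That tests registry entry, not the exclusion list.

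A reader might also infer four stronger things that the documents do not support:
- *Only the ICD-10 half operates.* The sentence naming ICD-10 describes registry entry. Both tables list both systems, and a patient who still carries a listed 295 or 296 code is caught.
- *A quantified loss of power.* This needs the share of orders from patients who should be excluded, which is not given, and an assumption that the tool leaves those orders unchanged, although the alert and its 30 pill-day default would apply to them. The 108 pill-days is the difference detectable with 80% power, not an expected effect. Setting one 360 pill-day quetiapine order against it (360/108 = 3.3) describes any such order, not this problem.
- *Bias between arms.* Physicians are randomized and one eligibility rule applies to both arms.
- *A contradiction over Parkinson's disease.* That exclusion has its own sentence and does not rely on Table 2, so its absence there is expected. What is missing is a stated code and a precedence rule, since G20 is a Table 1 entry code.

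**Conclusion.** The inconsistency between text and table is established from the documents. One of the four excluded groups has no ICD-10 code, bipolar disorder has three F31 codes only, and two of the 13 ICD-10 rows are dementia codes that qualify patients under Table 1. The text and both tables cannot all be applied as printed and yield the population described.

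The effect on the trial is conditional. If the alert, baseline counts and outcome extraction use Table 2 as printed, patients coded only under an unlisted ICD-10 code stay eligible, and target patients with G30.9 or F02.80 are lost. The number in the first group is unknown and probably small. The number in the second is also unknown, and the 12-month rule does not limit it. What is at stake is whether the analysed population is the one the plan describes; no between-arm bias or specific power loss is shown. The plan is wrong as written on this point, and the correction is cheap.

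**What to change.** In this order:
1. Complete the ICD-10 half of Table 2 for the groups the text names: F20.x, F25.x, F28, F29, F30.x and all F31.x.
2. Remove G30.9 and F02.80 from Table 2, or justify them.
3. State the code used for the Parkinson's exclusion (G20).
4. Only then state that exclusion codes take precedence over Table 1 entry codes, which settles F22 and G20. Stating precedence while G30.9 and F02.80 remain would exclude dementia patients the trial is aimed at.
5. Use this one list for the EHR alert, the baseline counts and strata, and the outcome extraction. If a different list is already loaded in the EHR, print that list and reconcile it with the text.

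The silent run described under Intervention Implementation is a convenient place to check the list against the text.

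The cost is a table correction, an update to the EHR code list and a re-run of the historical extract. The count of eligible patients will change, and the count of 149 physicians may change with it.

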## Intervention

We applied theoretically grounded behavioral economic methods to design an EHR CDS to reduce low-value antipsychotic prescriptions in adults with ADRD at UCLA Health. The EHR CDS tool was designed with input from a multidisciplinary team including a geriatrician, a palliative care specialist, a primary care general internist, a quality officer, informatics specialists, and two behavioral economists. The study team previously presented the proposed intervention in an iterative fashion to several stakeholder teams including physicians, informaticists, and health system leaders. The final intervention was approved by the UCLA Health System Primary Care Council (which includes patient representation), Alert Committee, and the Ambulatory Operations Advisory Group.

The intervention was designed based on a growing body of scientific evidence that multicomponent interventions are more likely to succeed than single-component interventions to reduce low-value care. The intervention is an EHR CDS that will include three components: 1) evidence from Choosing Wisely™ guidelines that encourage the clinician to avoid prescribing antipsychotics by highlighting increasing patient mortality risk and thereby appealing to the physician's desire for non-malfeasance; 2) prompts to incorporate IDEA! strategy resources on how caregivers can best manage a patient's behavioral disturbance non-pharmacologically, which will be available in the EHR to include in the patient's after

visit summary; and 3) for physicians who do not cancel their prescription order, an automatic default to a low dosing and low number of pill days prescribed in the order set (30 pill-days). The study team consulted a pharmacist expert (GC) on appropriate defaults for antipsychotics in terms of dosing, frequency, and number of pills supplied. For example, currently in the UCLA EHR quetiapine defaults to 25 mg by mouth once daily 90 tabs x 3 refills, totaling 360 pill-days. The study team will change the default to 25 mg by mouth once daily 30 tabs with no refills, totaling 30 pill-days. Physicians will be free to increase amounts as they desire and thus this EHR CDS will not include a “hard stop.” The study team opted against the hard stop in acknowledgement of the clinical complexity of this vulnerable patient population and in recognition of the fact that an outright ban on such prescriptions may have unintended consequences including but not limited to endangerment of caretakers or cohabitants. The EHR CDS tool will fire when the eligible physician places a new antipsychotic order for an eligible patient. Once the CDS tool fires and the physician places the order for either the original dose or a lower dose, the patient becomes no longer eligible due to having an active antipsychotic order. Therefore, it will not fire for prescription renewals.

### Intervention Implementation

We designed and pilot tested the EHR CDS in the informatics laboratory, which is led by the Chief Medical Informatics Officer. The CDS tool was also pilot tested among the research team, to assess correct activation and smooth functionality. The study team specifically designed the intervention to seamlessly fit within the EHR to minimize workflow disruption by only adding one additional click if accepting the intervention to avoid prescribing, and two clicks if rejecting the intervention in order to place the order. All UCLA Health clinicians will be alerted via email (through the usual mechanism to highlight new EHR tools at UCLA Health System) to the availability of the IDEA! handout that can be used for post-visit instructions to support non-pharmaceutical approaches to ADRD behavioral symptoms. The study team will pilot test the intervention to run silently in the EHR background just prior to activation in order to ensure proper activation of the EHR CDS tool. Just before the onset of the EHR intervention, the Principal Investigator (CS, geriatrician) will send a notification email to all physicians in the intervention arm to “prime” the physicians by notifying them they prescribed antipsychotics for patients with dementia in the past year, informing them of the upcoming EHR CDS rollout, and highlighting non-pharmacologic alternatives including the IDEA! handout.

### Data Collection Methods

Information sources will include: 1) administrative data found in the UCLA EHR; 2) survey data collected from clinicians in the intervention group; and 3) manual medical record review for patients with ED, falls, or death within 90 days of intervention exposure to assess for potential unintended consequences

## Statistical Analysis Plan

### Randomization & Blinding

A statistician not involved in data collection will randomize each eligible clinician to the intervention or control group; physicians will remain in the same arm of the study throughout the entire study period. The randomization of clinicians will be stratified by the number of new antipsychotic prescriptions during the baseline year: 1 vs. 2–3 vs. 4 or more new prescriptions. The randomization of the clinicians was incorporated into the EHR, tagging the providers as either EHR Intervention or EHR Control in a list created for this intervention. The study team will randomize physicians rather than patients to minimize

contamination. Contamination occurs when a physician sees a patient in the intervention arm at one time point, learns from the intervention that ordering antipsychotic medications is wrong and/or difficult, and then avoids prescribing these medications in the future, even when seeing a patient in the control arm. Because physicians will on average receive the intervention 1–2 times during the study period, inter-physician contamination will be minimal. Moreover, the CDS tool will only trigger for a new antipsychotic order, defined as an antipsychotic prescription for a patient who has not had an active antipsychotic prescription within the previous 12 months. This intervention will be implemented as part of a quality improvement effort; clinicians will not be blinded to receiving the intervention.

### [Primary Outcome](#)

The primary outcome will be the cumulative total of new antipsychotic prescription days supplied by clinicians per eligible patient in the 12 months after the intervention rollout date compared to the prior 12-months, in the intervention versus control groups regardless of the number of visits the provider receives.

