### [Statistical Analyses](#)

The study protocol follows SPIRIT international guidelines and will follow CONSORT guidelines when reporting the trial results. The complete trial protocol can be accessed in the supporting information files. Specifically, the study team will report descriptive statistics to characterize the sample of patients and clinicians included in the study. The study team will review patient charts to display the time series of new antipsychotic prescriptions during the 12 months before intervention rollout, and the 12 months after rollout. Each patient will be monitored for 90 days after their encounter with a physician in either the intervention or control arm, so the follow up period could last up to 90 days after the completion of the trial. The analysis of the primary outcome—total prescription pill-days—will utilize a physician-level linear regression model, with heteroscedasticity-robust standard errors, following prior published approaches. The model will include a fixed effects study arm (intervention vs. control) and baseline number of new prescriptions, adjusting for physician-level characteristics including physician gender and specialty. Analysis of secondary outcomes will proceed similarly, with the sensitivity analyses using different distributions and link functions as appropriate (e.g., a Bernoulli distribution with a logit link for the death outcome). To ensure equal consideration of outcomes among both groups, the study team will include 90-day follow-up for each outcome measure. A p-value of less than 0.05 will be considered

statistically significant. All analyses will follow the intention-to-treat principle and will be performed using SAS v. 9.4 (SAS Institute Inc., Cary, NC).

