### Sample Size

Power was evaluated using a simulation study. In each simulation, a data set was constructed, combining actual prescribing data from mid-2019 through mid-2020 with simulated data from the subsequent year. The number of total pill days per clinician in the subsequent year was simulated to preserve the mean and standard deviation across clinicians from the prior year, with an assumed year-to-year correlation within clinicians of 0.90. We have previously observed that a small number of providers do a large amount of prescribing, and a large number of prescribers do very little prescribing. The small number of physicians who are likely to continue their high levels of prescribing, leading to high correlation. Clinicians were then randomized into intervention and control arms, with the intervention arm's number of pill days reduced by a constant amount. A linear regression of year 2's number of pill days was fitted with study arm and year 1's number of pill days as predictors. Heteroskedasticity-robust standard errors were used to compute p-values. Significance was defined as a p-value less than 0.05 evaluating the study arm effect in the model, and power was estimated as the percentage of simulations in which a significant difference was obtained. We performed 10,000 simulations to estimate power. Based on historical data, we estimate that about 65% of physicians included in our randomization list will see an eligible patient during the study period. We thus expect our analytic sample to include data from 96 physicians. With 48 physicians randomized to each arm, we will have 80% power to detect a mean reduction of 108 pill days, which is feasible. This simulation power analysis was performed using R v. 3.6.2 (<http://www.r-project.org/>).

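### The primary outcome is stated on three scales that do not agree; only the physician total matches the planned model and the 108 pill-day power figure

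*Combined protocol and SAP*

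**What the plan says.** All references are to the combined protocol and SAP.

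- **Study Aims** (hypothesis): the intervention will lower clinicians' "pill days per patient prescribed". The denominator is patients who received a prescription.
- **Primary Outcome** (definition): "the cumulative total of new antipsychotic prescription days supplied by clinicians per eligible patient" over the 12 months after rollout, "compared to the prior 12-months, in the intervention versus control groups", whatever the number of visits. This can be read as a sum over eligible patients or as a ratio with eligible patients in the denominator.
- **Statistical Analyses** (model): the primary outcome is named as "total prescription pill-days", and its analysis "will utilize a physician-level linear regression model". No patient denominator, offset or weight is given. On baseline: "The model will include a fixed effects study arm (intervention vs. control) and baseline number of new prescriptions", with gender and specialty as further physician-level adjustments.
- **Sample Size** (power): "The number of total pill days per clinician in the subsequent year was simulated". A constant is subtracted in the intervention arm, and year 2 pill-days are regressed on arm and year 1 pill-days. The result is 80% power for a mean reduction of 108 pill-days with 48 physicians per arm.

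No section links the three wordings or says how a patient denominator would be counted.

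**The concern.** The tool is meant to act in two ways: some orders are cancelled, and those that go ahead start from a smaller default supply. A physician total picks up both.

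A mean over patients who were prescribed does not do so reliably, because a cancelled order leaves the numerator and the denominator together. It also conditions on an event after randomisation that the intervention is designed to change, so the patients being averaged are no longer comparable between arms. It has no value for a physician who cancels every order. That case is realistic: Inclusion Criteria expects more than 75% of physicians to see the tool only once or twice a year, so one or two cancellations can empty the denominator.

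A mean per eligible patient avoids those faults, since the patient stays in the denominator when an order is cancelled. It is still a different quantity from the one modelled and powered. A reader who checks the result against the stated hypothesis or outcome definition would be looking for a number that the planned analysis does not produce.

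**Working it through.** **Inputs.** Inclusion Criteria: 149 eligible physicians. Sample Size: 65% expected to see an eligible patient, 96 analysed, 48 per arm, 108 days, 80% power, year-to-year correlation 0.90, significance level 0.05 (sidedness not stated; two-sided assumed). Intervention: quetiapine default supplies of 360 (current) and 30 (new) pill-days, used here only as example order sizes.

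**1. The plan's own figure.** 149 × 0.65 = 96.85, in line with the 96 planned. The 80% cannot be reproduced independently because no standard deviation is given, but the implied value can be back-solved:

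- residual SD = 108 / [(1.960 + 0.842) × √(2/48)] = 108 / (2.802 × 0.2041) ≈ 188.9
- between-physician SD = 188.9 / √(1 − 0.90²) = 188.9 / 0.4359 ≈ 433 pill-days

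A 4,000-run simulation of the Sample Size regression with robust standard errors at SD 433 gave 78.7% power with a normal baseline and about 78% with a skewed one. So 108 is coherent as a difference in physician totals if the SD is near 433. Over assumed SDs of 250 to 800, power runs from 99.8% to 33%.

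**2. The same cancellation on three scales.** One physician, two eligible patients, one order each (assumed). Each cell shows the value without and then with the cancellation.

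| Case | Physician total | Mean per prescribed patient | Mean per eligible patient |
|---|---|---|---|
| Two 360-day orders, one cancelled, other unchanged | 720 → 360 (−50%) | 360 → 360 (0%) | 360 → 180 (−50%) |
| Orders of 360 and 30, the 360 cancelled | 390 → 30 (−92.3%) | 195 → 30 (−84.6%) | 195 → 15 (−92.3%) |
| Orders of 360 and 30, the 30 cancelled | 390 → 360 (−7.7%) | 195 → 360 (+84.6%) | 195 → 180 (−7.7%) |
| Two 360-day orders, both cancelled | 720 → 0 (−100%) | 360 → 0/0, undefined | 360 → 0 (−100%) |

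The mean per prescribed patient can stay flat, fall, rise or cease to exist, depending on which order is cancelled. The total falls in every case. The mean per eligible patient follows the total in percentage terms here, but its differences in days are half as large.

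**3. Does 108 carry over to a per-patient scale?** For a physician with k patients in the denominator, a fall of 108 in the total is 108/k per patient: 108, 54 or 27 days for k = 1, 2 or 4 (assumed counts). The documents give no number of eligible patients per physician. If k varies between physicians, the conversion is not a single rescaling either. The per-patient equivalent of 108 therefore cannot be stated.

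**4. The comparison with the prior 12 months.** The outcome definition compares pill-days with the prior 12 months. The simulation honours this by adjusting for year 1 pill-days. The planned model adjusts for the baseline number of new prescriptions, not baseline pill-days. Saying that the prior-year comparison enters through the planned model's baseline adjustment would therefore misdescribe that model as it stands.

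**The case against.** The strongest reply is that the tested quantity is already fixed. Statistical Analyses names the total in the same sentence as the model, and Sample Size simulates that quantity. The outcome definition also opens with a cumulative total supplied by clinicians and sets the number of visits aside, so its reference to eligible patients may simply be loose wording for whose prescriptions are counted.

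Much of this stands. A reader might infer from the three wordings that the scale could be chosen after the results are seen. The documents do not support that, because the analysis section commits to the total and no section plans a per-patient mean. A reader might also infer that every per-patient scale misses cancelled orders. That is untrue of a mean per eligible patient, and even the mean per prescribed patient moves when orders differ in size (step 2).

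The reply does not remove the contradiction. The patient denominator remains in the outcome definition, the hypothesis uses a different one, and setting visits aside rules out a per-visit scale but not a per-patient scale. A physician-level regression could be run on a per-patient mean, so the form of the model alone does not settle the reading.

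**Conclusion.** The point holds as an inconsistency in how the primary outcome is stated, and should be fixed. The planned test itself is not shown to be faulty.

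The size is illustrative: with one of two equal 360-day orders cancelled, the total falls by 50% and the mean per prescribed patient by 0%. That rests on assumed order sizes and counts. The size of the discrepancy in the trial cannot be computed, because the documents give neither cancellation rates nor numbers of eligible patients per physician.

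A reader might also conclude that 108 is wrong. The documents do not show that: it is coherent as a difference in physician totals, and applies to that scale only. Which physicians enter the analysis is a separate question and is not judged here.

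**What to change.** 1. In Study Aims and Primary Outcome, define the primary outcome as each physician's total new antipsychotic pill-days supplied to eligible patients in the 12 months after rollout, with 0 for an analysed physician who supplies none, compared between arms. Remove both per-patient denominators.
2. In Sample Size, label 108 pill-days as a difference in mean physician totals.
3. In Statistical Analyses, include the physician's pill-days in the prior 12 months as a baseline covariate, as the power model already does. This gives the comparison with the prior 12 months a defined place in the analysis.

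The cost is a few sentences and one added model term, computed from pill-day data for the 12 months before rollout, a period the plan already covers in its time series of new prescriptions. The downside is that totals also reflect how many eligible patients a physician sees. Randomisation balances this on average, and the baseline covariate partly adjusts for it.
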